#### **2 STUDY OBJECTIVES**

#### 2.1 Primary Objectives

Primary Outcome Measures:

- Donor specific antibody testing at Month 6
- Cell surface cytokine secretion in response to donor cell antigen by direct and indirect stimulation at Month 6
- Cell surface cytokine secretion in response to CMV and EBV antigens by direct and indirect stimulation at Month 6
- Immunophenotyping to determine overall immune profile at Month 6
- Survival and rejection in patients switched to belatacept at 12 months post transplant as compared with patients treated with conventional therapy at our center.

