#### 3.1.1 Duration of Study

The duration of the study is 6 months, with the possibility to extend an additional 6 months. The decision to participate in an additional 6 months of belatacept administration will be based on patient preference.

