	Defined Cell Population	FITC	PE	PerCP	APC	Pac	PE-
						Blue	Cy7
1	Central/effector	CD57	CCR7	CD3	CD45RA	CD8	CD4
	memory, naïve T cells						
2	Activation, memory	CD45RA	CCR5	CD3	CD95	CD8	CD4
3	Activation, effectors	CD45RA	HLA-DR	CD3	CD38	CD8	CD4
4	NK cells	CD161	CD94	CD3	CD56	CD16	
5	B cells	CD19	CD27	CD20	CD38	CD3	
6	T regs	FoxP3	CD103	CD4	CD25	CD3	

In addition we will analyze rates of rejection and patient and graft survival at 6 and 12 months post transplant as compared with patients receiving conventional immunosuppression regimens at our center.

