#### 3.3 Criteria for Evaluation

Primary Measures:

- Donor specific antibody testing at Month 6
- Cell surface cytokine secretion in response to donor cell antigen by direct and indirect stimulation at Month 6
- Cell surface cytokine secretion in response to CMV and EBV antigens by direct and indirect stimulation at Month 6
- Immunophenotyping to determine overall immune profile at Month 6
- Patient and functional graft survival in stable renal transplant recipients

Secondary Outcome Measures:

- Donor specific antibody testing at Months 1 and 3
- Cell surface cytokine secretion in response to donor cell antigen by direct and indirect stimulation at Months 1 and 3 (and month 12 if continuing in study)
- Cell surface cytokine secretion in response to CMV and EBV antigens by direct and indirect stimulation at Months 1 and 3 (and month 12 if continuing in study)

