#### 4.2 Analyses

#### Immunologic mechanisms

Primary endpoints will be patient immune analysis at 24 weeks (end of study) as compared with control patients at a comparable time point for DSA, frequency of alloantigen and viral antigen reactive cells, and frequency of the immunophenotypes described above, comparison to be performed by Mann Whitney U test. In addition, a comparison will be made between patients' baseline and week 24 levels. ANOVA repeated measurement analysis will be used to evaluate immune measurements taken over time as compared with control patients

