#### Efficacy and safety

As an additional primary analysis, subject and graft survival at 6 months will be determined within each group. GFR measured at baseline and months 1, 3, 6, and 12 months will be descriptively summarized. Cumulative rates of acute and chronic rejection, and chronic allograft nephropathy, will be summarized, as well as incidence of post-transplant diabetes.

All AEs and SAEs since transplantation will be summarized for the patients receiving belatacept. For the control patients, rates of rejection, PTLD, and death will be summarized.

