#### 7.2.4 Standard Study Visits

a) To occur on Weeks 4, 12, and 24 as well as week 48 for those electing to continue in the study

- b) Assess and record AEs pretreatment.
- c) Check and record any changes in concomitant medications
- d) Obtain weight and vital signs

e) Draw whole blood for immunology analysis, to be sent by courier to the Immunogenetics Center

- f) DSA testing
- g) EBV PCR testing

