#### 7.2.5 Early Termination Procedures

For randomized, transplanted, and treated subjects who received at least 1 dose of study medication and discontinue from study medication for any reason, if informed consent continues to be provided we will continue to perform study procedures scheduled for weeks 4, 12, and 24 including an additional study lab draw at the time of drug discontinuation if it is not within 14-days of one of the above listed study visits

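### The clinical primary outcome has conflicting time points (12 months post transplant in 2.1, 6 months in 4.2), and no stated data source gives 12-month status for subjects outside the extension or for controls

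*Combined protocol and SAP*

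**What the plan says.** Four sections of the combined protocol and SAP define the clinical primary outcome differently.

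- **2.1 Primary Objectives:** "Survival and rejection in patients switched to belatacept at 12 months post transplant", compared with conventionally treated patients at the center.
- **3.1.3:** "we will analyze rates of rejection and patient and graft survival at 6 and 12 months post transplant". Neither time point is ranked above the other.
- **3.3 (and the synopsis):** "Patient and functional graft survival in stable renal transplant recipients". There is no time point, and rejection is absent.
- **4.2, Efficacy and safety:** "As an additional primary analysis, subject and graft survival at 6 months will be determined within each group". The origin of the 6 months is not given. Rejection is to be summarized cumulatively, with no time point.

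On follow-up, 3.1.1 sets a 6-month study with an optional further 6 months: "The decision to participate in an additional 6 months of belatacept administration will be based on patient preference". Section 7.2.4 schedules the standard visits: "To occur on Weeks 4, 12, and 24 as well as week 48 for those electing to continue in the study". The last column of the 7.1 table carries the same restriction. For subjects who stop drug, 7.2.5 says "we will continue to perform study procedures scheduled for weeks 4, 12, and 24" and nothing later. Section 4.2 treats week 24 as the close of the study.

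**The concern.** A primary outcome should have one time point, one origin and a data source that reaches everyone in the analysis. Here the objectives and the analysis section name different times, and the visit schedule does not reach the later one for every subject. Someone following the schedule exactly would not collect the 12-month outcome in 2.1 for all 20 subjects.

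The missing origin also matters. If 6 months runs from transplant, a subject switched at month 3 contributes only 3 months on belatacept. If it runs from the switch, the same subject is assessed at month 9 post transplant.

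At stake is whether the survival and rejection result can be interpreted as the pre-stated primary comparison. Similar rejection rates in the two groups is one of the outcomes to be tested in 1.1.

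**Working it through.** The plan states no power, event rate or dropout figure for this outcome, so there is no figure of its own to reproduce. The check is calendar arithmetic plus an illustration of size.

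**Inputs from the documents**
- Entry 0 to 3 months after transplant (7.2.1), taken as day 0 to day 91.
- Last visit outside the extension at week 24 = day 168 from entry; extension visit at week 48 = day 336 (7.2.4).
- 20 subjects (3.4).
- First-year acute rejection of about 10%, quoted for a cyclosporine-based regimen (7.3.6).

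**Time without scheduled contact outside the extension** (30.44 days per month)

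| Entry | Week 24 post transplant | Gap to day 365 |
|---|---|---|
| Day 0 | 168/30.44 = 5.5 months | 365 − 168 = 197 days = 6.5 months (54% of the year) |
| Day 91 | 259/30.44 = 8.5 months | 365 − 259 = 106 days = 3.5 months (29% of the year) |

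**Extension visits do not fix the endpoint either.** Week 48 falls at 336/30.44 = 11.0 months post transplant for entry at day 0 and at 427/30.44 = 14.0 months for entry at day 91. It precedes day 365 for entry within the first 365 − 336 = 29 days.

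**Subjects affected.** Extension uptake is not in the documents. Assuming uptake of 75%, 50% or 25%, the number outside the extension is 20 × (1 − uptake) = 5, 10 or 15. If their 12-month status were truly unknown, the best-to-worst-case range for an event rate would be 5/20, 10/20 or 15/20, that is 25, 50 or 75 percentage points.

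**Events likely to fall in the gap.** Assume that the 10% figure applies to these converted subjects and that the hazard is constant: −ln(0.90) = 0.105 per year. Expected rejections = n × 0.105 × gap/365.

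| n outside extension | Gap 106 days | Gap 197 days |
|---|---|---|
| 5 | 0.15 | 0.28 |
| 10 | 0.31 | 0.57 |
| 15 | 0.46 | 0.85 |

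The expected number is below one throughout. One event is 1/20 = 5 points. For comparison, 18 of 20 event-free has an exact 95% interval of 68% to 99%.

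**Start of counting.** Exclusion criterion 9 in 5.2 removes anyone with biopsy-proven acute rejection in the first three months, and a subject must be alive to enroll. Belatacept subjects are therefore alive and free of biopsy-proven rejection up to entry. Controls are matched on age, sex, donor type and DSA level (3.1.3), with no such condition. Counting both groups from transplant would give the belatacept group guaranteed event-free time that controls need not have.

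**The case against.** The best reply is that 12-month clinical status is meant for everyone. Month-12 DSA and cytokine assays are limited to subjects who continue, whereas month-12 survival and rejection (2.1, 3.1.3) and month-12 GFR (4.2) carry no such limit. Rejection screening and biopsy follow center practice (6.2.6.5, 7.3.3.1), and the 7.1 figure text describes a 12-month study. Section 3.1.3 already commits to both time points, and the efficacy analysis in 4.2 is descriptive. This is also a small mechanistic study whose main outcomes are immunologic.

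Most of that stands, and it rules out three stronger readings.

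- A reader might infer that the 12-month result will cover only subjects who chose the extension and will therefore favor belatacept. The plan does not say so. Events through week 24 are collected even after drug is stopped, and follow-up of control outcomes is not described, so no direction can be argued.
- A reader might infer that one time point can be reported and the other suppressed. Section 3.1.3 plans both; what is open is which one is primary.
- A reader might want the mention of vital and graft status struck from the withdrawal criterion in 6.6. That mention can be read as a high bar, met only when even status collection is against the subject's interest. Removing it could make full withdrawal easier.

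What the reply does not supply is a sentence naming the data source, its cut-off, or its application to non-extension subjects and controls. It also leaves 2.1 and 4.2 in conflict.

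**Conclusion.** The concern holds as a defect in the definition and collection of a primary outcome. The time points in 2.1 and 4.2 disagree, the origin in 4.2 is missing, rejection has no analysis time, and the schedule leaves 106 to 197 days before day 365 uncovered for subjects outside the extension. The day counts rest only on the entry window and visit weeks.

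The practical size is probably small. Center records are likely to hold the status of most subjects, and the expected 0.2 to 0.9 rejections in the gap depend on assumed uptake, a constant rate and a borrowed cyclosporine figure. No bias in either direction is demonstrated. The change is worth making because it is cheap and because the outcome is labeled primary.

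**What to change.** In 2.1, 3.1.3, 3.3 and 4.2, name 12 months post transplant as the single primary time point for survival and rejection, as 2.1 already does, and label 6 months supportive with its origin stated. Add to 3.1.3 and 4.2:

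> Death, graft loss and rejection (Banff 97) are taken from center records through day 365 after transplant for every treated subject, whatever the treatment or extension status, and from the same source for the 20 matched controls. Each control must be alive, with a functioning graft and free of biopsy-proven rejection, at the time since transplant at which the matched subject entered. Events in both groups are counted from that time. The number with unknown status is reported by group.

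Leave 6.6 as it is.

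The cost is amendment wording, a line in the consent form and about 40 chart reviews (20 + 20) at one center. Treatment and sample size do not change. One limitation follows: subjects who decline the extension spend part of the year off study belatacept, so the 12-month result describes the switch strategy and not 12 months of belatacept.

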#### 2.2 Secondary Objectives

Secondary Outcome Measures:

- Donor specific antibody testing at Months 1 and 3 (and month 12 if continuing in study)
- Cell surface cytokine secretion in response to donor cell antigen by direct and indirect stimulation at Months 1 and 3 (and month 12 if continuing in study)
- Cell surface cytokine secretion in response to CMV and EBV antigens by direct and indirect stimulation at Months 1 and 3 (and month 12 if continuing in study)

#### **3 STUDY DESIGN AND EVALUATION**

#### 3.1 Study Design

This study is an open label, single center clinical trial. All subjects will also receive ongoing immunosuppression with mycophenolate mofetil and corticosteroid maintenance therapy.

#### 3.1.1 Duration of Study

The duration of the study is 6 months, with the possibility to extend an additional 6 months. The decision to participate in an additional 6 months of belatacept administration will be based on patient preference.

#### 3.1.2 Overview

This is an open label, single center clinical trial. All subjects will have undergone kidney transplantation with induction immunosuppression and will be on maintenance therapy with a CNI (tacrolimus or cyclosporine) plus mycophenolate mofetil and corticosteroid maintenance therapy at the time of enrollment. 20 subjects with evidence of CNI toxicity (see definition below) in the first three months after transplant will be enrolled to switch to the belatacept regimen. These enrolled subjects will be compared with 20 matched patients from an ongoing observational study of kidney transplant patients at our center.

All subjects will also receive induction with basiliximab and a background maintenance immunosuppressive regimen of MMF and corticosteroids.

Study patients will receive intravenous belatacept at 5mg/kg every two weeks at day 1 and weeks 2, 4, 6, and 8, and then monthly at months 3, 4, and 5. At month 6 patients may elect to continue for an additional six-month period of belatacept administration

#### 3.1.3 Primary Outcome Measures and Justification

Patients switched to the belatacept-based regimen will be compared to a group of matched patients on standard CNI-based immunosuppression regimen on the following primary outcome measures: (1) the donor specific antibody level, (2) the frequency of alloantigen and viral antigen reactive cells as measured by cell surface cytokine analysis, and (3) the frequency of immunophenotypes described below at Month 6. Matching will be performed based on age within 10 years, sex, deceased versus living transplant, and DSA level at time of enrollment.

The intent is to investigate differences in these measures as a means to determine the immunologic mechanism of action of belatacept. These endpoints were selected based on previous research showing that these measures are key determinants of immune function in transplant patients. In addition, baseline levels at time of enrollment of these endpoints will be compared with results from months 1, 3, and 6, as well as month 12 if patients elect to continue for an additional 6 months of belatacept therapy. Month 6 will be used as the primary measure of outcome for the immunologic assays, with months 1, 3 and 12 if applicable as the secondary measures.

To perform these mechanistic studies, blood from subjects will be collected at each study time point as described below and peripheral blood mononuclear cells (PBMCs) will be isolated and frozen for future analysis.

For analysis of response to alloantigen stimulation, PBMCs will be incubated with either intact donor cells or membrane preparations from donor cells to test either direct or indirect immunity, respectively. Following incubation, a cocktail of fluorescent-conjugated monoclonal antibodies will be added to detect relevant immunologic subclasses of cells as well as relevant surface cytokines and the percentage of each lymphocyte subset will be analyzed using flow cytometry according to previously published protocols developed at the UCLA Immunogenetics Center [7].

For analysis of response to viral antigens, PBMCs will be extracted and stored as described above using well-characterized CMV or EBV antigens for stimulation during the incubation period using a similar protocol adapted for detection of relevant antiviral immune lymphocytes.

Overall immune profile will also be analyzed by immunophenotyping using multiparameter flow cytometry using the panels described below:

	Defined Cell Population	FITC	PE	PerCP	APC	Pac	PE-
						Blue	Cy7
1	Central/effector	CD57	CCR7	CD3	CD45RA	CD8	CD4
	memory, naïve T cells						
2	Activation, memory	CD45RA	CCR5	CD3	CD95	CD8	CD4
3	Activation, effectors	CD45RA	HLA-DR	CD3	CD38	CD8	CD4
4	NK cells	CD161	CD94	CD3	CD56	CD16	
5	B cells	CD19	CD27	CD20	CD38	CD3	
6	T regs	FoxP3	CD103	CD4	CD25	CD3	

In addition we will analyze rates of rejection and patient and graft survival at 6 and 12 months post transplant as compared with patients receiving conventional immunosuppression regimens at our center.

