10.5 Institutional Review Board (IRB)
10.6 Records Retention
11 GLOSSARY OF TERMS AND LIST OF ABBREVIATIONS
11.1 Glossary of Terms
11.2 List of Abbreviations
12 REFERENCES

#### **1 INTRODUCTION**

1.1 Research Hypothesis

**Primary Hypothesis:** 

Conversion from CNI-based therapy to belatacept will be safe and effective for prevention of rejection, with a significant impact on antibody and T cell-mediated immune response as compared with control patients as measured in peripheral blood at 6 months after belatacept conversion.

Outcomes to be tested:

- Belatacept-treated subjects will not have a greater incidence of SAEs as compared with control patients
- Belatacept-treated subjects will have similar rates of acute rejection as compared with control patients
- Belatacept-treated subjects will have a lower donor-specific antibody level at 6 months compared with control patients
- Belatacept-treated subjects will have a decrease in the frequency of alloantigen specific T cells over time as compared with control patients
- Belatacept-treated subjects will have a decrease in the frequency virus specific T cells over time as compared with control patients
- Belatacept-treated subjects will have a greater percentage of naïve and central memory T cells and a lower percentage of activated T cells as compared with control patients

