#### 4 STATISTICAL METHODOLOGY 4.1 Data Set Descriptions

Data sets will be generated for all patients enrolled in the study with recorded frequency of alloantigen specific cells at weeks 0, 4, 12, and 24 after study start after both direct and indirect stimulus, frequency of anti CMV and anti EBV specific cells at weeks 0, 4, 12, and 24, and frequency of cell populations as determined by immunophenotyping analysis at weeks 0, 4, 12, and 24. A representative group of 20 control patients receiving standard immunosuppressive medications will be identified from an ongoing observational study at our center using matching criteria described above. Patient matching will be performed in a blinded fashion. The ongoing observational study at UCLA is led by [name] and all patients undergoing kidney transplantation at UCLA are eligible for enrollment for an ongoing evaluation of immunologic predictors of rejection. PBMCs have been aliquoted and stored from these patients at time points post transplantation similar to those described in this protocol so they will be an ideal source for comparative analysis.

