5.2 Exclusion Criteria Gender and Reproductive Status

1) WOCBP who are unwilling or unable to use an acceptable method to avoid pregnancy for the entire study period and for up to 8 weeks after the last infusion.

2) Women who are pregnant or breastfeeding

3) Women with a positive pregnancy test on enrollment or prior to study drug administration

4) Males unwilling or unable to use an adequate method of contraception for the entire study period and for up to 8 weeks after the last infusion of study medication

Immunologic status

5) Subjects with PRA  $\ge$  30% at time of transplant

6) Subjects with zero HLA antigen mismatched donors (either from related or unrelated donor)

7) Subjects with any prior solid organ transplant (including kidney)

8) Subjects receiving a concurrent solid organ (heart, liver, pancreas) or cell (islet, bone marrow, stem cell) transplant

9) Subjects with a history of biopsy-proven acute rejection post-transplant (humoral or cellular) in the first three months post transplantation

Infection related risks

10) Subjects who are hepatitis C antibody-positive or polymerase chain reaction

(PCR)-positive for hepatitis C

11) Subjects who are hepatitis B surface antigen-positive or PCR-positive for hepatitis B

12) Subjects with known human immunodeficiency virus (HIV) infection

13) Subjects with active tuberculosis (TB) requiring treatment within the previous 3 years or any subject who previously required triple (or more) combination therapy for TB.

14) Subjects who are EBV antibody negative and have received grafts from EBV antibody positive donors.

Prohibited Therapies and/or Medications

15) Subjects who have used any investigational drug within 30 days prior to the Day 1 visit

16) Subjects previously treated with belatacept

18) Use of mTOR inhibitors at any time after transplantation

Other Exclusion Criteria

18) Prisoners or subjects who are compulsorily detained (involuntarily incarcerated) for treatment of either a psychiatric or physical (e.g., infectious disease) illness must not be enrolled into this study.

19) Subjects who have difficult i.v. access or other reasons that would likely preclude medication administration

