6.2.6.4 Prophylaxis medications

Medications commonly in use for antibiotic prophylaxis will be continued following normal transplant protocols in place at our center. These medications include sulfamethoxazole/trimethoprim and valganciclovir or acyclovir. To summarize, patients who are antibody negative for CMV (R-) receiving transplants from CMV antibody positive donors (D+) will receive valganciclovir prophylaxis for the first 6 months post transplant at 900 mg daily by mouth, or as adjusted for their renal function. Patients with other CMV serology combinations (D-/R-, D+/R+, and D-/R+) will receive acyclovir 400 mg daily by mouth for the first 3 months post transplant. In addition, single-strength trimethoprim-sulfamethoxazole is given daily by mouth for the first 3 months post transplant.

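### The primary CMV and EBV T-cell comparison pools seropositive and seronegative recipients in one rank test, and the EBV D+/R- exclusion is not stated for controls, so a true decrease is easily missed

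*Combined protocol and SAP*

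**What the plan says.** Section 3.3 lists among the primary measures "Cell surface cytokine secretion in response to CMV and EBV antigens by direct and indirect stimulation at Month 6". Section 3.1.3 makes it a between-group comparison of "the frequency of alloantigen and viral antigen reactive cells as measured by cell surface cytokine analysis", and section 1.1 gives it a direction: "Belatacept-treated subjects will have a decrease in the frequency virus specific T cells over time as compared with control patients".

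Controls are 20 patients "identified from an ongoing observational study at our center using matching criteria described above", where "all patients undergoing kidney transplantation at UCLA are eligible for enrollment" (section 4.1). The match is defined once, in 3.1.3: "Matching will be performed based on age within 10 years, sex, deceased versus living transplant, and DSA level at time of enrollment". CMV and EBV serostatus are not in that list.

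Section 5.2, item 14, excludes from the trial "Subjects who are EBV antibody negative and have received grafts from EBV antibody positive donors", and 6.4.2.2 repeats this. No section says whether item 14, or any other section 5 criterion, applies to controls.

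Section 4.2 assigns the week 24 comparison to a Mann-Whitney U test with no stratification or covariate. It adds a baseline-to-week-24 comparison and a repeated-measures ANOVA against controls; neither mentions serostatus.

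CMV serology is already in use at the centre. Under 6.2.6.4, "patients who are antibody negative for CMV (R-) receiving transplants from CMV antibody positive donors (D+) will receive valganciclovir prophylaxis" for six months, while the other serology combinations receive acyclovir for three.

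**The concern.** A recipient never exposed to a virus starts with few or no memory T cells against it, so serostatus is likely to be the largest single source of variation in these assays. Section 1.2 itself raises the question of how much pre-existing virus-specific memory matters. The planned test nevertheless ranks exposed and unexposed recipients together.

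Two separate problems follow. For either virus, the seronegatives add variation unrelated to belatacept and dilute any effect in patients who have memory cells to lose. For EBV, a group of patients barred from the belatacept arm may be present among the controls. If those controls respond less, the control distribution moves down, towards the place where the hypothesis expects the belatacept group to lie. A real decrease could then be missed on a primary endpoint.

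**Working it through.** **The plan's own figure.** Section 3.4 gives 20 patients with no effect size, SD, alpha or power, so there is nothing to reproduce. For scale, with everyone seropositive, the effect detectable with 80% power at two-sided 5% is (1.960 + 0.842) × √(2/20) = 0.886 SD, or 0.886/√0.955 = 0.907 SD for Mann-Whitney.

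**Inputs.** From the documents: 20 v 20, Mann-Whitney, no stratification. Assumed, because the documents are silent: two-sided 5%, no dropout, seropositive share 50–90%, log-scale SD 1, seronegatives 3 SD below seropositives (2 SD as a check), drug effect in seropositives only.

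**CMV, error rate.** When both groups share one seroprevalence, the pooled test rejects in 4.6–5.0% of simulated trials with no drug effect. The overall error is nominal.

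**CMV, power at 60% seropositive (12 of 20 per group on average), effect 0.93 SD.**
- Among seropositive pairs, P(belatacept < control) = Φ(0.93/√2) = 0.745. These pairs move U by 12 × 12 × 0.245 = 35.2.
- Mixed pairs (12 × 8 = 96 each way) add 96 × [Φ(3/√2) − Φ(2.07/√2)] = 96 × (0.983 − 0.928) = 5.3. Total 40.5.
- Null SD of U = √(20 × 20 × 41/12) = 36.97. Expected z = 40.5/36.97 = 1.10, and power ≈ Φ(1.10 − 1.96) = 19%.
- Van Elteren, weights 1/(N+1) by stratum: mean 35.2/25 = 1.41; variance (12 × 12 × 25/12)/25² + (8 × 8 × 17/12)/17² = 0.480 + 0.314 = 0.794. z = 1.41/0.891 = 1.58, and power ≈ Φ(1.58 − 1.96) = 35%.

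Simulation agrees with both. For a 0.9 SD effect the pooled test has 12%, 27% and 59% power at 50%, 70% and 90% seropositive. With only 2 SD separation it has 16%, 35% and 63%.

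**CMV, chance imbalance.** For two independent Binomial(20, p) counts:

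| Seropositive share | Differ by ≥4 | Differ by ≥5 |
|---|---|---|
| 50% | 26.8% | 15.4% |
| 60% | 25.8% | 14.5% |
| 70% | 22.6% | 11.9% |
| 80% | 16.4% | 7.3% |

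With no drug effect, the pooled test's false-positive rate is about 7% at 12 v 16 seropositives, 13% at 10 v 15 and 26% at 10 v 16. The stratified test holds 4–5% at all three splits.

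**Matching without stratifying.** With serostatus fixed at 12 v 12, U varies less than its pooled null variance assumes, so the test becomes conservative: with no effect, a 14 v 14 split rejects in 0.2% of runs. Power for a 0.93 SD effect falls from about 19% to about 7% (5.5% for 0.9 SD).

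**EBV.** Assume all belatacept patients are seropositive and a fraction f of controls are EBV-naive. Power of the pooled test for a true 0.9 SD decrease:

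| f | Power | False result of belatacept higher, no effect (nominal 2.5%) |
|---|---|---|
| 0 | 77% | 2.6% |
| 5% | 63% | 4.6% |
| 10% | 45% | 7.4% |
| 20% | 20% | 18% |

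The table lets the number of naive controls vary by chance. With exactly 4 of 20 naive, power is about 13%. A check for that case: seropositive pairs move U by 20 × 16 × 0.238 = 76.1 towards belatacept lower. The 20 × 4 = 80 pairs with naive controls move it back by 80 × 0.431 = 34.5. The net is 41.6, so z = 1.13, against 400 × 0.238/36.97 = 2.57 with no naive controls.

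**The case against.** A reader might infer that CMV serostatus confounds the comparison and would pass for a belatacept effect. The documents do not support that. Nothing in them makes CMV serostatus differ systematically between the groups, and under a common seroprevalence the test keeps its 5% level. The 13% and 26% rates are conditional on particular unlucky splits; a difference of 5 or more arises in only 7–15% of draws at 80–50% seropositive.

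A reader might also infer that controls are exempt from the EBV exclusion. The protocol does not say so. It describes who may join the observational study and how matches are made, and is silent on section 5. That objection stands, but silence combined with an open source leaves the gap.

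The EBV figures may overstate the loss. Controls infected by Month 6 may respond and would soften it. Item 14 still admits EBV-negative recipients of EBV-negative organs, so the belatacept group need not be wholly seropositive.

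The longitudinal analyses are a real mitigation. The viral hypothesis concerns change over time, control cells are stored at similar time points, and persistent seronegatives contribute little change. But 3.1.3 and 4.2 make the Month 6 comparison primary, and that comparison uses no baseline.

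Finally, the study is declared exploratory with no power claim. That lowers the stakes, but a primary endpoint with a stated direction and 20 patients per group has little information to spare.

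**Conclusion.** The point holds as a loss of sensitivity, with a possible one-directional EBV bias. It does not hold as a general claim of inflated false positives. For CMV, the pooled test has roughly half the power of a stratified one under the central assumptions (19% v 35%) and is exposed to chance imbalance. For EBV, the control group may include patients whom the trial excludes, and this would tend to hide the hypothesised decrease, by an amount ranging from modest (63% power with 5% naive) to severe (13–20% with 20% naive). The size rests on assumed seroprevalence, separation and effect; the documents fix none of these. The structural facts come directly from the text: serostatus is absent from the match and the test, and exclusion 14 is not stated for controls. The longitudinal analyses repair this only in part.

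**What to change.** 1. In 4.2, replace the Mann-Whitney test for the viral endpoints with a van Elteren test stratified by recipient serostatus for the virus concerned (CMV for CMV responses, EBV for EBV responses).
2. In 3.1.3 and 4.1, require control candidates to meet exclusion 14 and the immunologic-status exclusions in 5.2 (items 5 to 9).
3. Tabulate CMV and EBV donor/recipient serostatus by group.

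Adding serostatus to the match is optional. It should not be done while keeping the pooled test, because that lowers power (about 19% to 7% at 60% seropositive).

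The cost is a somewhat smaller control pool and slightly more analysis work. No new visit, sample or patient is needed. CMV serology already drives prophylaxis, and trial patients' EBV serology is needed for item 14; that control EBV serology is on file is an assumption to confirm.
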